#### 7.5. **ECGs**

ECGs will be performed in triplicate for some visits and assessment time points. The average of these multiple non-missing measurements for these visits and assessment time points will be used for analysis.

QTcF (QT correction according to Fridericia's formula) will be calculated as follows based on the QT interval and the RR interval (= 60/HR(heart rate)):

$$QTcF = \frac{QT}{\sqrt[3]{RR}}$$

Number and percentage of patients in the following categories will be summarized by visit for QTcF:

- >450 msec
- >480 msec
- >500 msec
- change from baseline >30 msec
- change from baseline >60 msec

The categories above are not mutually exclusive.

By-patient listings of ECG data will be provided.

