14.5.3. Other Safety Endpoints

Twelve lead ECGs will be collected and analyzed for evidence of cardiac toxicity, especially prolongation of QT interval. Change in LVEF from baseline will be summarized. Vital signs will be summarized with descriptive statistics at each visit and time point at which they are collected. Shift tables may be created.

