# 4.4. Multiple Assessments for the Same Assessment Time Point

In general, no by-visit analyses is planned for this study, unless otherwise indicated for a specific parameter.

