# 4.12. Data Display Characteristics

Data displays produced for this study will include summary tables, data listings, and figures. Data listings will be produced for all recorded data as described in Section 5, Section 6, and Section 7. Summary tables will be produced as specified in Section 5, Section 6, and Section 7. Additional data listings will be produced for outcome measures that involve extensive procedures to derive the analyzed outcomes. Figures will be produced when specified in Section 5, Section 6, and Section 7.

Data listings will report the data recorded on the eCRF or derived for each patient. Data will be ordered by patient number, and date/time of assessment. When expedient, additional levels of ordering hierarchy may reflect subsets of assessments within patient. Data listings will not display patient initials.

The summary statistics displayed will be a function of the type of data associated with the summarized assessment. Unless stated otherwise in relevant sections, Section 5, Section 6, and Section 7, continuous data will be summarized with the number of non-missing values, mean, standard deviation, minimum, median, and maximum. Categorical data will be summarized with

the number of non-missing values and the numbers of values equal to each of the possible values. Percentages of patients with each of the possible values will be calculated from the number of patients in the corresponding analysis population, unless stated otherwise. Some continuous variables may also be grouped into categorical levels and evaluated in frequency tables.

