#### 7. SAFETY ANALYSES

The safety analyses will be performed on the Safety population. The assessments/events up to 30 days (inclusive) of the last dose of study drug or prior to the start of a new anti-cancer treatment, whichever occurs first, will be analyzed, unless otherwise stated. Baseline is defined as the last non-missing observed measurement prior to the first dose of study drug.

Unless otherwise stated, summaries of safety data will be presented for each dose level of IMGC936, combined RP2P dose (6mg/kg) as well as for overall of all patients in the Safety population.

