# 7.3. Clinical Laboratory Results

Laboratory test results (including hematology, coagulation, serum chemistry, and urinalysis) and abnormal laboratory values will be presented in data listings.

CTCAE Version 5.0 laboratory grades will also be presented. CTCAE grades will be derived based on laboratory results and will not factor in clinical evaluations.

Shift tables summarizing the changes from baseline to worst post-baseline values (high or low, as applicable) in severity of laboratory grades will be summarized by CTCAE grade.

Clinically significant values in liver function tests (LFTs) will be summarized by the following categories, using the maximum lab value among visits. The denominator for the summaries will be the number of patients who had at least 1 non-missing post-baseline value within 30 days of the last dose of study drug or prior to the start of a new anti-cancer treatment, whichever occurs first. The categories for each test are not mutually exclusive:

- Aspartate aminotransferase (AST)
  - $> 3 \times ULN$
  - $> 5 \times ULN$
  - $> 10 \times ULN$
  - $> 20 \times ULN$
- Alanine Aminotransferase (ALT)

- $> 3 \times ULN$
- $> 5 \times ULN$
- $> 10 \times ULN$
- $> 20 \times ULN$
- AST or ALT
  - $> 3 \times ULN$
  - $> 5 \times ULN$
  - $> 10 \times ULN$
  - $> 20 \times ULN$
- Total bilirubin (TBL)
  - > ULN
  - $> 2 \times ULN$
- Alkaline phosphatase (ALP)
  - > 1.5 × ULN
- (AST or ALT) and TBL (concurrent)
  - AST or ALT  $> 3 \times ULN$  and TBL  $> 1.5 \times ULN$
  - AST or ALT  $> 3 \times ULN$  and TBL  $> 2 \times ULN$
- (AST or ALT) and ALP and TBL (concurrent)
  - AST or ALT  $> 3 \times$  ULN and ALP  $< 2 \times$  ULN and TBL  $> 2 \times$  ULN

Here, concurrent means that all the associated LFTs must be from the same visit.

Results from pregnancy tests will be provided in listings.

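### The QTcF categories are summarised only by visit, so no planned table counts the participants who ever cross a threshold on treatment

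*SAP*

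**What the plan says.** SAP 7.5 averages replicate ECGs within a time point ("The average of these multiple non-missing measurements for these visits and assessment time points will be used for analysis"), derives QTcF by Fridericia's formula, and then states: "Number and percentage of patients in the following categories will be summarized by visit for QTcF". The categories are above 450, 480 and 500 msec and a rise from baseline above 30 and 60 msec. The section ends with "By-patient listings of ECG data will be provided". It has no worst-value or any-visit row, and no other SAP section supplies one.

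Four other places bear on this:

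- Protocol 14.5.3 says that ECGs are analysed for cardiac toxicity, "especially prolongation of QT interval". It makes shift tables optional.
- SAP 4.4 sets the general rule: "In general, no by-visit analyses is planned for this study, unless otherwise indicated for a specific parameter". QTcF is one of the exceptions.
- SAP 7.3 classifies liver tests "using the maximum lab value among visits" and states the denominator. Its laboratory grade shifts use the worst post-baseline value.
- SAP 4.12 says that percentages "will be calculated from the number of patients in the corresponding analysis population" unless stated otherwise. SAP 7.5 states nothing else, and SAP Section 7 says: "The safety analyses will be performed on the Safety population".

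**The concern.** In a first-in-human study, the natural question for a QTcF threshold is how many participants crossed it at any time on treatment. A by-visit table answers a different question: how many were above it on a given occasion. Two participants who cross at different visits never appear together in one row. A reader who takes the largest row as the incidence will usually read it too low, and a reader who adds the rows may count one participant several times.

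The rows also leave a choice open. Dosing-day visits have a pre-infusion and an end-of-infusion ECG (Protocol Appendix 1 and Appendix 2, footnote d in each). SAP 7.5 averages replicates but does not say which time point places a participant in the visit row. SAP 4.4, whose heading covers multiple assessments, gives no selection rule, so two programmers could produce different tables.

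**Working it through.** The plan states no QTcF rate, so there is no figure of its own to reproduce. The check has three parts.

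**1. Visits with an ECG after the first dose (Protocol Appendix 1 and Appendix 2, ECG footnotes)**

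- Schedule A: C1D1 (end of infusion), C1D8, C2D1, C3D1 and the end of treatment visit, so k = 5.
- Schedule B: C1D1 (end of infusion), C1D8, C1D15, C2D1, C3D1 and the end of treatment visit, so k = 6.

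**2. Direction**

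Let N be the Safety Population, n_j the number above the threshold at visit j, and E the number ever above it. Those flagged at visit j are a subset of those ever flagged, so n_j ≤ E and n_j/N ≤ E/N for every visit. Equality needs everyone who ever exceeds to do so at that visit. Also, E ≤ n_1 + … + n_k, with equality only if no participant recurs. The rows show neither overlap nor recurrence, so E cannot be recovered from them.

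The direction depends on the common denominator N. If the rows instead used only participants with an ECG at that visit, a late row could exceed the overall share. For example, with assumed counts, 1/20 = 5.0% at a late visit against 1/45 = 2.2% overall. SAP 4.12 makes N the default.

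**3. Possible size**

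Assume the same share p of N at each of k visits. Then:

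- lower limit (the same participants every time): p
- upper limit (different participants every time): k × p
- independent visits: 1 − (1 − p)^k

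| Schedule | p (assumed) | Lower | Upper | Independent |
|---|---|---|---|---|
| A, k = 5 | 1% | 1% | 5% | 1 − 0.99^5 = 4.9% |
| A, k = 5 | 3% | 3% | 15% | 1 − 0.97^5 = 14.1% |
| A, k = 5 | 5% | 5% | 25% | 1 − 0.95^5 = 22.6% |
| B, k = 6 | 1% | 1% | 6% | 1 − 0.99^6 = 5.9% |
| B, k = 6 | 3% | 3% | 18% | 1 − 0.97^6 = 16.7% |
| B, k = 6 | 5% | 5% | 30% | 1 − 0.95^6 = 26.5% |

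Readings from one participant are correlated, so the independent column is high. With equicorrelated normal readings and p = 3%, the ever share is the integral of 1 − Φ((z − √ρ·u)/√(1 − ρ))^k over a standard normal u, where z is the upper 3% point. This gives:

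| ρ (assumed) | k = 5 | k = 6 |
|---|---|---|
| 0.5 | 10.7% | 12.1% |
| 0.7 | 8.7% | 9.6% |
| 0.9 | 6.0% | 6.4% |

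Even at 0.9 the ever share is about twice the 3% in each row.

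**The case against.** The strongest reply is that the information is not lost. By-patient ECG listings are planned, and with 3 to 15 participants per escalation dose the count is easy to make by hand. Protocol 12.1.1 counts abnormal diagnostic results as adverse events, and SAP 7.2 counts each participant once at the worst grade, so a reported QT event would appear in the adverse event tables. No primary or secondary efficacy estimate, escalation rule or pausing rule uses the QTcF table. The SAP does not take the worst value everywhere either: vital-sign shifts in SAP 7.4 use the last post-baseline value.

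Much of this stands. A reader might infer that the plan makes the ever-exceed count unobtainable, but the listings contain it. What is missing is a planned summary. The adverse event route is only a partial substitute, because it depends on investigator reporting and does not use these five cut-offs.

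Three other inferences go further than the documents:

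- That every visit row must understate the share. A row can equal it, and the bound relies on the SAP 4.12 denominator.
- That unscheduled ECGs are excluded. The SAP is silent on how they are assigned to visits.
- That the gap should be sized on individual readings, 7 on Schedule A and 10 on Schedule B. The table is by visit, so 5 and 6 are the relevant counts.

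The size is also illustrative. The per-visit rate is assumed, and a constant share at every visit is a simplification in a relapsed or refractory population where some will stop before Cycle 3.

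**Conclusion.** The point holds as a gap in the planned summaries. SAP 7.5 gives QTcF exceedances by visit and nothing per participant across visits. Under the default denominator, each row is a lower bound on the share who ever exceed, and usually a strict one. At an assumed 3% per visit, the true share could be anywhere from 3% to 15% on Schedule A or 3% to 18% on Schedule B, and the table could not tell a reader where in that range it lies. That the rows cannot exceed the ever share follows from the denominator alone; the size rests on the assumed rate and on how far the same participants recur. This is a descriptive safety table, so no trial decision rule is affected. The change is still worth making, because QT prolongation is the stated focus of the ECG analysis and the SAP already uses the across-visit maximum for liver tests.

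**What to change.** In SAP 7.5:

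1. Add, for each of the five categories, a row for any post-baseline (worst) value per participant. Use all ECGs after the first dose, including C1D1 end of infusion and any unscheduled ECGs, and exclude the C1D1 pre-infusion ECG. Keep replicate averaging within a time point.
2. Apply the SAP Section 7 window: up to 30 days after the last dose or before new anticancer treatment, whichever comes first. Cite the Section 7 baseline (before the first dose). SAP 4.2 defines baseline by date, which would leave the C1D1 end-of-infusion ECG ambiguous.
3. State the denominator for the new row: participants with at least one post-baseline ECG in the window, and also a baseline value for the change categories. This follows the liver-test approach in SAP 7.3.
4. Present the by-visit rows by time point, pre-infusion and end of infusion. This removes the ambiguity and keeps the contrast between the two, which collapsing each visit to its worst value would hide.

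The cost is SAP wording, one row block and the split rows, with no new data collection. The reported exceedance rates may look less favourable.

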#### 7.6. Concomitant Medications

All medications and supportive therapy taken within 14 days prior to Cycle 1 Day 1 and through 30 days after last study treatment must be recorded on the appropriate eCRF. The identity of all medications, dosage, route of administration, frequency, duration of administration, and indication for use will be recorded in the appropriate sections of the eCRF.

Prior medications are defined as medications with a stop date prior to the first dose of study drug.

Concomitant medications are defined as medications which are taken during the course of study treatment and within 30 days of the last dose of study drug or before the start of a new anti-cancer treatment, whichever occurs first:

• Medications started before the first dose of study drug, but with a stop date after the first dose of study drug will be considered concomitant medications.

- Medications started before the first dose of study drug that are ongoing will be considered concomitant medications.
- Medications started after the first dose of study drug and within 30 days of the last dose of study drug or before the start of a new anti-cancer treatment, whichever occurs first, are considered concomitant medications.

Prior and concomitant medications will be coded using the September 2019 or later version of World Health Organization drug dictionary (WHO Drug). Summary tables will be provided for prior and concomitant medications.

Summary tables will be organized to display the anatomical main class of each coded medication (ATC Level 1 term) and, within that, the pharmacological subgroup (ATC Level 3 term) of the coded medication. The summary table will display number and percentage of patients who reported using at least 1 medication in each represented pharmacological subgroup. If a patient has more than 1 medication in the subgroup, the patient will be counted only once.

A complete listing of medications will be generated by patient. The listing will indicate which medications are prior and which are concomitant. The listing will display entries from the concomitant medications form, ordered within patient by start date. The listing will display the recorded term from the eCRF and the WHO Drug anatomical main class (ATC Level 1 term) and pharmacological subgroup (ATC Level 3 term).

#### 7.7. Concomitant Procedures

All procedures within 14 days before the Cycle 1 Day 1 through 30 days after last study treatment must be recorded on the appropriate eCRF. Prior procedures are defined as occurring before the first dose of study drug (by procedure date). Concomitant procedures are defined as procedures with a procedure date on or after the first dose of study drug, and within 30 days of the last dose of study drug or prior to the start of a new anti-cancer treatment, whichever occurs first.

Prior and concomitant procedures will be coded using MedDRA, associating lower-level terms with PT and SOC by the primary hierarchy. Summary tables will be provided for prior and concomitant procedures. The tables will display number and percentage of patients who reported at least 1 procedure in each SOC represented in the eCRF data. Within each SOC, the tables will display number and percentage of patients reporting at least 1 concomitant procedure as designated by PT.

A complete listing of procedures will be generated. The listing will indicate which procedures are prior and which are concomitant. The listing will display entries from the concomitant procedures form, ordered within patient by date of procedure. The listing will display the recorded term from the eCRF and the SOC and PT.

## 7.8. Physical Examination

Physical examination results will be presented in data listings.

#### 7.9. ECOG PS

ECOG PS results will be presented in data listings. Baseline ECOG PS will be summarized in disease characteristics table (Section 5.1.4).

#### **7.10. ECHO/MUGA**

Left ventricular ejection fraction (LVEF) results at screening and End of Treatment visit are collected via eCRF. The screening results will be summarized in disease characteristics table (Section 5.1.4). Change in LVEF from baseline to End of Treatment visit will be summarized. All results will be presented in data listings.

## 7.11. Ophthalmic exam and ocular symptom assessment

Baseline and post treatment ophthalmic exam and ocular symptom assessment results are collected via eCRF. Findings during these assessments are reported as adverse events and summarized in TEAE and ocular TEAE tables. Best correct visual acuity (BCVA) changes are summarized in the table of BCVA shift from baseline to the worse post baseline.

## 8. QUALITY OF LIFE (QOL)

Not applicable.

#### 9. IMMUNOGENICITY

The immunogenicity analyses will be covered by a separate, independent analysis plan.

#### 10. BIOMARKERS

The biomarker analyses will be covered by a separate, independent analysis plan.

# 11. PHARMACOKINETICS (PK)

The PK analyses will be covered by a separate, independent analysis plan.

